Trial: Mindfulness-based Cognitive Coping for ADRD Caregivers

ClinicalTrials.gov ID: **NCT05979922**

Date: **07/24/2025 (updated)**

Investigator: **[name]**

Research Site:

Photozig, Inc.
[name]
[name]
[name]

Project Summary

Alzheimer's Disease (AD) is a devastating illness for patients, families, and society. Most of the care of AD patients rests on shoulders of informal caregivers, largely untrained to undertake the caregiving role, bearing a high level of distress, and suffering deterioration in physical health and psychological well-being.

There are millions of Americans providing care to AD patients, experiencing high rates of depressive symptoms (30%), stress (59%), associated risks for cardiovascular diseases, and many other adverse health effects. For example, in separate studies, hospitalization and emergency department visits were more likely for dementia caregivers than any other types of caregivers.

The severity of AD caregiving is influenced by several factors, such as intensity of dementia symptoms in AD patients, how challenging distressful situations are perceived by caregivers, and available resources. Although information and programs about Alzheimer's Disease are available to the public, an essential missing tool is how to deal with depressive symptoms in an effective manner, as they are very common and demanding.

In this project we will implement the new Mindfulness-based Cognitive Coping (MCC) intervention, and enable easy access with our mobile app, called Caring Mind App (CMA), providing an effective cost-effective intervention for caregivers to reduce their stress and depressive symptoms. The MCC intervention is built upon the Mindfulness-Based Cognitive Therapy (MBCT), which has been effective to treat individuals with major depressive disorder, with the integration of caregiving coping strategies from our past studies to help caregivers to overcome stressful situations in their caregiver role.

We will finalize the MCC curriculum, develop the complete app, and evaluate its effectiveness in a randomized clinical trial; resulting in a novel intervention that integrates MCC content, an effective training to reduce depressive symptoms and psychological stress, and a mobile app to be deployed to millions of families struggling with Alzheimer's Disease.

Protocol

Overview:

1. Recruit subjects: caregivers of individuals with Alzheimer's Disease or other dementia will be recruited.
2. Randomize subjects: participants will be assigned to the study group or the control group.
3. Collect pre-data: Before intervention, we will collect pre-data to establish the baseline status of participants.
4. Deploy treatments: For both study and control groups, we will send instructions and materials.
5. Collect post-data: We will collect post-treatment data after 3 months.

Research Participants: 150 dementia family caregivers (planned enrollment) will be recruited:

Inclusion Criteria:

- Care for an individual with Alzheimer's Disease or Related Dementia (ADRD).
- Own a smartphone or tablet and have Internet access.
- Minimum age of 18 years old.
- Able to read and speak English.
- Spend at least 8 hours/week caring for a person with dementia.
- Plan to stay in the area for six months.

Exclusion Criteria:

- Severe psychological or physical illness.
- Cognitive impairment or any serious medical problem that interferes with caregiving role.
- Caring for ADRD patient with a life expectancy less than six months.
- Unwillingness to participate in all aspects of the study.

Informed consent will be obtained, and participants will receive a stipend for their participation.

Methods: The effectiveness investigation of the Caring Mind App (CMA) will be implemented with a pre-post randomized trial of 3 months. As it takes 3 months to complete the entire program, post testing will happen about 3 months after pre-testing. The trial will have two levels: the CMA treatment package; and a control condition comprised of existing educational programs, information for caregivers, and other resources. Outcome measures of both groups will be recorded at baseline and after 3 months.

- CMA Condition (75 subjects): Participants will receive the Caring Mind mobile app containing the MCC curriculum.
- Control Condition (75 subjects): Participants will receive a traditional educational/resources program, containing a workbook and online resources.

Procedures: Participants will receive and complete informed consent. After initial assessment, subjects will be randomized to either CMA or the control condition, and instructions will be distributed. After 3 months, all subjects will be interviewed for the post-intervention assessment.

Statistical Analysis Plan

Main study hypothesis: “CMA will alleviate depression (measured by CES-D) and decrease stress (measured by PSS)”.

Main Outcome Measures:

- Depression: level of Depressive Symptoms: their presence and strength will be assessed using the Center for Epidemiological Studies Depression scale (CES-D); This is a 20-item measure that asks about the frequency of depressive symptoms (affective, psychological, and somatic) within the past week.
- Overall Perceived Psychological Stress: the 10-item Perceived Stress Scale (PSS) measures overall appraisals of stress in the past month.

Analysis: Our hypotheses will be tested by analyzing the change scores (subtracting the baseline scores from the value obtained at 3 months) for the outcome measure (CES-D and PSS) and comparing the results of CMA with the control condition in order to determine the efficacy of the intervention. We will determine if subjects in CMA had a significant decrease in level of depression and reduced stress, when compared to the control group. We'll use univariate ANOVA (analysis of variance) to determine the level of significance for these measures.

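### Does a single post-test at about 3 months make the PSS measure stress during the program rather than after it, and so undermine the stress comparison?

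*Combined protocol and SAP*

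**What the plan says.** Methods gives the program length and the clock together: "As it takes 3 months to complete the entire program, post testing will happen about 3 months after pre-testing". It then limits the assessments to two: "Outcome measures of both groups will be recorded at baseline and after 3 months". Overview step 5 says "We will collect post-treatment data after 3 months", and Procedures says "After 3 months, all subjects will be interviewed for the post-intervention assessment". Procedures also places the start of the intervention after the pre-test: "After initial assessment, subjects will be randomized to either CMA or the control condition, and instructions will be distributed".

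The two main outcomes look back over different periods. In the SAP, under Main Outcome Measures, "the 10-item Perceived Stress Scale (PSS) measures overall appraisals of stress in the past month", while the CES-D "asks about the frequency of depressive symptoms (affective, psychological, and somatic) within the past week". The Analysis paragraph uses one change score per outcome, the 3-month value minus baseline. There is no assessment window, no rule for interviews held early or late, and no later follow-up. The main hypothesis is that the app will alleviate depression and decrease stress. It names no time after the program ends.

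**The concern.** The program lasts 3 months and starts after pre-testing, and the post-test comes about 3 months after pre-testing. Read literally, the post-test falls at the end of the program, or before it if materials arrive late. A PSS that covers the preceding month then describes the last third of the program, not life afterwards, which sits awkwardly with the post-treatment and post-intervention labels. The CES-D is much less exposed, because only the last week is involved.

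If benefit grows as the curriculum is worked through, the PSS averages in weeks when part of the program was still to come. The PSS contrast would understate the end-of-program effect, and the trial could miss a real reduction in stress. With no window stated, the period that the PSS describes would also vary with the interview date.

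**Working it through.** **Inputs.** From Methods: program 3 months, post-test about 3 months after pre-testing, 75 per arm. From the SAP: PSS recall one month, CES-D recall one week. Assumed, because the documents do not give them: 3 months = 91 days, a month = 30 days, no start lag, two-sided 5% test, no drop-out, and the shape of the benefit over time. The documents state no power calculation, so there is no planned figure to reproduce.

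**Overlap of recall with the program (days 0 to 91).**
- Interview at day 91: PSS recall is days 61 to 91, 30 of 30 days on-program. CES-D recall is days 84 to 91, 7 of 7.
- Day 84: PSS recall is days 54 to 84, 30 of 30.
- Day 105: PSS recall is days 75 to 105, so 91 − 75 = 16 of 30.
- Day 121: PSS recall is days 91 to 121, 0 of 30.

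On the nominal schedule the overlap is real. An early interview does not change the count. A late one reduces it.

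**Share of the end-of-program benefit that the day-91 score carries.** Let f be the benefit at a given program day, scaled to 1 at day 91, and take the mean of f over the recall period.
- Complete by day 61: PSS 1.00, CES-D 1.00.
- Linear: PSS (61 + 91)/2/91 = 76/91 = 0.835; CES-D (84 + 91)/2/91 = 87.5/91 = 0.962.
- Quadratic: PSS (91³ − 61³)/(3 × 91² × 30) = 526590/745290 = 0.707; CES-D (91³ − 84³)/(3 × 91² × 7) = 160867/173901 = 0.925.

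**Two variations, equally compatible with the documents.**
- Linear benefit, with recall weight rising linearly from zero at day 61 to the interview: the weighted mean day is 61 + (2/3) × 30 = 81, so the PSS share is 81/91 = 0.890.
- Benefit peaking at day 61 and fading to 80% of that peak by day 91: the mean over the recall period is (1.0 + 0.8)/2 = 0.9, so the PSS share is 0.9/0.8 = 1.125. The score then overstates the end-of-program effect.

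**Power.** For a two-sample t test with 75 per arm, 80% power corresponds to d = 0.460. At d = 0.460 × share:

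| Assumption | PSS share | PSS power | CES-D share | CES-D power |
|---|---|---|---|---|
| Complete by day 61 | 1.00 | 80% | 1.00 | 80% |
| Linear | 0.835 | 65% | 0.962 | 77% |
| Quadratic | 0.707 | 51% | 0.925 | 74% |
| Linear, recent days weighted more | 0.890 | 70% | – | – |
| Peak, then fade | 1.125 | 88% | – | – |

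The 0.460 is solved backwards from 80% power and is not a target in the plan, so these percentages show sensitivity and do not forecast the trial's power.

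**What the analysis estimates.** The baseline PSS covers the month before pre-testing, which precedes the intervention. The change score therefore sets a month before the program against, nominally, its last month. The between-arm difference in that change is a decrease in stress relative to control, which is what the hypothesis asks about.

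**Order of steps.** Overview step 2 reads "Randomize subjects: participants will be assigned to the study group or the control group" and comes before the collection of pre-data, whereas Procedures randomises after the initial assessment. Both orders put pre-data before the intervention, so the discrepancy does not affect the timing question.

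**The case for a change.** The strongest case for acting is that what the PSS measures depends on an interview date the plan leaves open, and that the wording would be cheap to add before the data are analysed. A start lag makes dilution worse. With materials arriving half a month after pre-testing (an assumed figure) and an interview at exactly 3 months, PSS recall covers program months 1.5 to 2.5. Under linear build-up the share is then 2.0/3 = 0.667, and at an assumed d of 0.5 power falls from 87% to 53%. A linear build-up is a natural guess for a curriculum worked through step by step.

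The overlap on the nominal schedule stands, and so does the absence of a window. The claim that the post-test falls at or before the end of the program does not stand as a fact. It appears only when both intervals are fixed at exactly the same length. Methods says about 3 months and gives program completion as the reason for the timing, so a post-test somewhat later is within the plan. With no start lag, an interview at 3.5 months has half its PSS recall after the program and all of its CES-D recall.

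The possible remedies also bring little. Restating the anchor and adding a window would write down detail without changing the main result. An analysis limited to in-window interviews would select on something that happens after randomisation. A further PSS a month after the program would need an extra contact to answer a question about persistence that the hypothesis does not ask.

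**Conclusion.** No change to the plan is needed. The 3-month PSS is best read as stress over roughly the last month of the program, and the CES-D as depressive symptoms over roughly its last week. Measuring at the end of the program is a legitimate trade-off: results come promptly, at the cost of some on-program time in the longer recall period. Both arms are interviewed on the same schedule, so the overlap creates neither bias nor false-positive results.

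Any effect on sensitivity is confined mainly to the PSS and its direction is unknown. In the zero-lag scenarios above, PSS power runs from 51% to 88% around an assumed 80%. That range depends on build-up shape, recall weighting and effect size, none of which the documents supply. A start lag would matter only if it were appreciable and the interview were not allowed to run correspondingly late. The missing window is a gap that analysts fill sensibly by keeping every 3-month interview in the comparison of change scores. The SAP already states both recall periods, so a reader can interpret the result correctly.

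### The only planned test is an ANOVA on change scores with no baseline adjustment; ANCOVA on the same data would be more precise and would remove the effect of chance baseline imbalance

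*Combined protocol and SAP*

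**What the plan says.** The Analysis paragraph of the Statistical Analysis Plan is the whole of the statistical methods. The hypotheses are tested by "analyzing the change scores (subtracting the baseline scores from the value obtained at 3 months") and by "comparing the results of CMA with the control condition in order to determine the efficacy of the intervention". The test is a "univariate ANOVA (analysis of variance) to determine the level of significance for these measures". No covariate, stratification factor, ANCOVA, mixed model or sensitivity analysis is named anywhere.

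The Methods paragraph of the Protocol states that "Outcome measures of both groups will be recorded at baseline and after 3 months", so the baseline CES-D and PSS scores will be available. Planned enrolment is 150, with 75 in each arm. No alpha, power, effect size, SD, correlation or dropout rate is given.

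**The concern.** A one-way ANOVA with two groups is a two-sample t-test, here on the change score. Subtracting baseline resembles adjusting for it, but it amounts to assuming a slope of exactly 1 for the 3-month score on the baseline score. If the SDs at the two times are equal, the true slope is rho, which is below 1 for any scale that is not perfectly reproducible. Change scores then over-correct, and an arm that starts higher by chance tends to show the larger fall even if the intervention does nothing.

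Two things are at stake for both main outcomes. The treatment estimate is noisier than the collected data allow, in a trial of 75 per arm with no stated power calculation and so no known margin to absorb the loss. And if the arms differ at baseline, the estimate is biased in a predictable direction given that difference. Leaving adjustment unspecified also invites a choice after the fact if the baselines turn out to differ.

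**Working it through.** **Inputs from the documents.** Two arms, 75 per arm (75 + 75 = 150, which agrees with planned enrolment); one assessment at baseline and one at 3 months; change score analysed by ANOVA. The plan gives no power calculation to reproduce.

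**Assumptions, none in the documents.** Equal SDs at both times, alpha 0.05 two-sided, all 75 per arm analysed, rho from 0.3 to 0.8. Effects are in units of the SD of the raw score.

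**Precision.** Per-participant variance in units of SD²:
- change score: 1 + 1 − 2·rho = 2(1 − rho)
- ANCOVA residual: 1 − rho²
- ratio, ANCOVA to change score: (1 − rho²) / [2(1 − rho)] = (1 + rho)/2

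At rho 0.5 the variances are 1.00 and 0.75, a ratio of 0.75. Matching ANCOVA's precision with change scores would take 1/0.75 = 1.33 times as many participants. Power is from the noncentral t distribution, with 148 degrees of freedom for the ANOVA and 147 for ANCOVA. At 75 per arm the effect detectable with 80% power is 0.460 residual SDs, which is multiplied by √[2(1 − rho)] for the change score and, to rounding, by √(1 − rho²) for ANCOVA.

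| rho | variance ratio | equivalent extra participants | detectable difference, change → ANCOVA (SD) | ANCOVA power where change score has 80% | power for a 0.4 SD effect, change → ANCOVA |
|---|---|---|---|---|---|
| 0.3 | 0.65 | 54% | 0.54 → 0.44 | 94% | 54% → 72% |
| 0.5 | 0.75 | 33% | 0.46 → 0.40 | 90% | 68% → 80% |
| 0.6 | 0.80 | 25% | 0.41 → 0.37 | 88% | 78% → 86% |
| 0.7 | 0.85 | 18% | 0.36 → 0.33 | 86% | 88% → 93% |
| 0.8 | 0.90 | 11% | 0.29 → 0.28 | 84% | 97% → 98% |

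Below rho 0.5 the change score is noisier than the 3-month score alone: at rho 0.3 its variance is 2(1 − 0.3) = 1.4 times as large.

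**Simulation.** With 6,000 trials per rho, power for a 0.4 SD effect was 53%, 68%, 89% and 97% (change score) against 72%, 80%, 93% and 98% (ANCOVA) at rho 0.3, 0.5, 0.7 and 0.8. Type I error was 4.6% to 5.2% for the change score and 4.5% to 5.4% for ANCOVA.

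**Baseline imbalance.** The standard error of the baseline difference between arms is SD·√(2/75) = 0.163 SD. Given a baseline difference D, the change-score contrast is shifted by −(1 − rho)·D. If the SD is 10 points (assumed), the standard error is 1.63 points and a 2-SE imbalance is 3.3 points. The shift is then 1.6, 1.3 and 1.0 points at rho 0.5, 0.6 and 0.7.

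Under no treatment effect, and given an imbalance of k standard errors, the absolute change-score test statistic is centred on k·√[(1 − rho)/2] with SD √[(1 + rho)/2]. At rho 0.5 and k = 2 these are 1.00 and 0.866. The upper tail is P(Z > 0.96/0.866 = 1.11) = 0.134 and the lower tail is negligible. With the normal cut-off of 1.96, conditional type I error is:

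| imbalance | rho 0.5 | rho 0.6 | rho 0.7 |
|---|---|---|---|
| none | 2.4% | 2.8% | 3.4% |
| 1 SE | 4.8% | 4.9% | 4.9% |
| 2 SE | 13.4% | 11.7% | 10.1% |

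Averaged over all imbalances this returns to 5%. Linear ANCOVA removes the dependence on the observed imbalance.

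**Equal SDs relaxed.** If the 3-month SD is k times the baseline SD, the two variances are 1 + k² − 2·rho·k and k²(1 − rho²). Their difference is (1 − rho·k)², which is never negative. At k = 1.2 and rho 0.7 they are 0.76 and 0.734, a ratio of 0.97 rather than 0.85.

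**The case against.** The strongest counter-argument is that the planned test is valid. Under randomisation a change-score ANOVA is unbiased on average and keeps its 5% type I error, as the simulation confirms. The raised conditional error rates belong to a 2-SE baseline imbalance, which arises in about 5% of trials per outcome; at 1 SE there is no inflation. This stands, and it makes the point one of efficiency and of conditional bias, not of an invalid trial.

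The size of the gain rests on figures the documents do not give. At rho 0.8 it is small (97% to 98% power for a 0.4 SD effect), and a larger SD at 3 months can nearly remove it. This also stands, but the direction does not change: the variance difference is a square, so ANCOVA loses no more than one degree of freedom, while at rho 0.3 to 0.5 the gain is substantial.

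The text does not expressly exclude covariates, so the absence of adjustment is read from silence. That is fair, but a univariate ANOVA on change with no covariate named is naturally read as unadjusted. If adjustment is intended, the plan still has to say so.

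Finally, the document is dated as updated 07/24/2025 and does not state trial status. Changing the main analysis once results have been seen by arm would be a post-hoc change. This limits when the fix can be made, not whether it is sound.

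**Conclusion.** The concern holds. The only test for both main outcomes leaves out a covariate that the trial already collects. With equal SDs the planned analysis gives up 10% to 35% of the variance for rho from 0.8 to 0.3. At rho 0.5 the loss is 25%, equivalent to forgoing 33% more participants. It also carries (1 − rho) of any chance baseline difference into the result. These sizes depend on the assumed rho, equal SDs, two-sided 0.05 and complete follow-up; the direction does not depend on rho or on equal SDs, apart from the one degree of freedom. The planned test is inefficient rather than invalid, so this is a change the plan should make, not one without which the trial fails.

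**What to change.** Replace the change-score ANOVA in the Analysis paragraph with ANCOVA, separately for CES-D and PSS: 3-month score as response, arm as factor, the same scale's baseline score as covariate. Report the adjusted mean difference with its 95% CI. Mean change per arm can stay as a descriptive summary. Using the change score as response with baseline as covariate gives the same treatment estimate, if the sponsor prefers to keep the language of change.

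The covariate should be unaffected by allocation. Procedures states that "After initial assessment, subjects will be randomized to either CMA or the control condition", but the Overview lists randomisation as step 2 and baseline data collection as step 3, saying only "Before intervention, we will collect pre-data to establish the baseline status of participants". The two should be reconciled so that baseline is clearly measured before randomisation.

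The cost is one sentence of wording, with no new data, visits or participants. The change should be made and dated before anyone sees outcomes by arm. If that point has passed, the planned analysis should stay primary and the ANCOVA be reported as a labelled post-hoc analysis.

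### The only planned test, an ANOVA on 3-month change scores with no analysis population or missing-data method stated, defaults to caregivers who have a post-test and can be biased by selective dropout

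*Combined protocol and SAP*

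**What the plan says.** The Analysis paragraph of the Statistical Analysis Plan sets out one method: "analyzing the change scores (subtracting the baseline scores from the value obtained at 3 months) for the outcome measure (CES-D and PSS", with the arms compared by univariate ANOVA. On timing, Methods says "Outcome measures of both groups will be recorded at baseline and after 3 months", so there is one post-baseline assessment and no interim value. Procedures states the intended follow-up: "After 3 months, all subjects will be interviewed for the post-intervention assessment". Planned enrolment is 150, with 75 in each condition.

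The documents do not define an analysis population or mention intention to treat. They give no expected dropout, no rule for a caregiver without a post-test, and no sensitivity analysis. Several provisions bear on retention: a stipend, a requirement to plan to stay in the area for six months, and the exclusion of caregivers whose patient is expected to live less than six months.

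**The concern.** A change score needs both values. If the 3-month value is missing, the caregiver drops out of the ANOVA even though a baseline CES-D and PSS were collected. With no other instruction, the analysis is of caregivers who have a post-test.

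This matters because retention could plausibly be related to the outcome. CES-D and PSS measure depression and stress, which may affect whether a burdened caregiver returns. The conditions also differ in kind, an app-based curriculum against a workbook and online resources, so equal dropout for the same reasons cannot be taken for granted. If caregivers who are doing badly leave CMA more often, an ineffective app can look better than it is. If caregivers with high baseline scores leave CMA more often, the change-score comparison moves the other way. Those with high baselines tend to fall most through regression to the mean, and CMA loses more of them.

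**Working it through.** **Inputs from the documents.** "150 dementia family caregivers (planned enrollment) will be recruited", 75 per arm (75 + 75 = 150). Outcome: 3-month value minus baseline. Test: univariate ANOVA. The plan states no dropout figure, so there is none to reproduce.

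**Assumed inputs.** SD of CES-D change 9; two-sided 0.05 (critical value 1.96); no true effect; dropout of 25% or 20% in CMA and 10% in control. A negative bias favours CMA.

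**Case A: leavers would have changed worse than completers, by the same amount d in both arms.**

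Bias = d × (p_control − p_CMA).

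SE = 9 × √(1/(75(1 − p_CMA)) + 1/(75(1 − p_control))).

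At 25%/10%, SE = 9 × √(1/56.25 + 1/67.5) = 1.62. At 20%/10%, SE = 9 × √(1/60 + 1/67.5) = 1.60.

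Chance of a false significant result favouring CMA = Φ(−1.96 − bias/SE), nominally 2.5%. The opposite tail is Φ(−1.96 + bias/SE).

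| Dropout CMA/control | d | Bias | False result favouring CMA | Two-sided error |
|---|---|---|---|---|
| 25%/10% | 3 | 3 × (−0.15) = −0.45 | 4.6% | 5.9% |
| 25%/10% | 5 | −0.75 | 6.7% | 7.5% |
| 25%/10% | 8 | −1.20 | 11.1% | 11.4% |
| 20%/10% | 3 | 3 × (−0.10) = −0.30 | 3.8% | 5.4% |
| 20%/10% | 5 | −0.50 | 5.0% | 6.1% |
| 20%/10% | 8 | −0.80 | 7.2% | 7.9% |

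With equal dropout and the same d in both arms, the bias is 0.

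**Case B: dropout depends only on baseline.** Suppose leavers' mean baseline is G points above completers', and the 3-month score rises by s per baseline point. Leavers' mean change then differs from completers' by −(1 − s) × G, so bias = (1 − s) × G × (p_CMA − p_control). At 25%/10%:

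- s = 0.6, G = 4: 0.4 × 4 × 0.15 = +0.24
- s = 0.5, G = 6: 0.5 × 6 × 0.15 = +0.45
- s = 0.4, G = 8: 0.6 × 8 × 0.15 = +0.72

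These are against CMA.

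**Simulation check.** 75 per arm, no true effect, baseline-to-3-month correlation 0.6, 5,000 runs per scenario. Bias is in SD of the score. The adjusted column is a regression on baseline among caregivers with a post-test.

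| What drives dropout | Dropout control/CMA | Change-score bias | Type I error | Adjusted bias |
|---|---|---|---|---|
| Nothing related to scores | 10%/30% | −0.00 | 5.3% | −0.00 |
| Baseline, both arms | 24%/24% | 0.00 | 4.6% | 0.00 |
| Baseline, both arms | 13%/33% | +0.07 | 7.0% | 0.00 |
| Baseline, CMA only | 20%/24% | +0.08 | 8.2% | 0.00 |
| 3-month score, both arms | 24%/24% | −0.00 | 5.4% | −0.00 |
| 3-month score, both arms | 13%/33% | −0.07 | 6.0% | −0.11 |
| 3-month score, CMA only | 20%/24% | −0.08 | 8.0% | −0.13 |

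Three things follow. Unequal dropout unrelated to the scores does no harm. Near-equal dropout can bias if the reasons differ by arm. Baseline adjustment removes the baseline-driven bias, but leaves the outcome-driven bias in place and in these scenarios makes it somewhat larger.

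**The case against.** The sponsor can fairly reply that the plan intends a post-test for everyone and takes steps to keep people in, so missing data may be few. That stands as a statement about data collection, but neither the intention nor the retention provisions say how to analyse a caregiver who is not reached.

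Four stronger readings are tempting, and the documents do not support them.

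- A reader might infer that the SAP orders leavers to be deleted. It does not. Exclusion follows by default from silence.
- A reader might infer that unequal dropout is enough to bias the result. It is not. Leavers must also differ from completers in their change.
- A reader might infer that the test compares only those who kept using the app with those who kept using the workbook. The 3-month interview is not conditional on use, so a non-user who is interviewed has a change score and is analysed.
- A reader might take the exclusion "Unwillingness to participate in all aspects of the study" as grounds for removing caregivers after randomisation. It stands in a list of eligibility criteria, and nothing extends it beyond entry.

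It is also fair to say that the illustrated biases are modest: at most 1.2/1.62 = 0.74 of a standard error in Case A and 0.72/1.62 = 0.44 in Case B. With a single post-test, ordinary baseline adjustment already removes the bias in Case B, so the choice of a repeated-measures model over simpler adjustment is partly preference.

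**Conclusion.** The gap is real but conditional. As written, the analysis defaults to caregivers with a 3-month interview, and no rule covers the others. The comparison can be biased if dropout is related to baseline or outcome and its rate or reasons differ by arm.

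At 25% against 10% dropout, the bias is 0.45 to 1.2 CES-D points towards CMA in Case A and 0.24 to 0.72 points against it in Case B. These figures rest on assumed dropout, SD, slope, gaps and alpha, none of which the documents give. The true size and direction are therefore unknown, and no PSS figure was worked out. A reader might conclude that the randomised comparison is lost, but nothing here shows that. The case for changing the plan is that the exposure is avoidable at very little cost.

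**What to change.** In the Analysis paragraph:

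1. Replace the change-score ANOVA with an analysis of all randomised caregivers in their assigned arm. Use a baseline-adjusted likelihood-based model of the baseline and 3-month scores with a common baseline mean, or multiple imputation by arm that includes baseline. Apply it to both CES-D and PSS. This removes baseline-driven bias, provided the relation to baseline is adequately modelled. It does not remove bias from dropout that depends on the unseen 3-month score.
2. For that, add one sensitivity analysis based on multiple imputation. Shift the imputed 3-month scores of CMA leavers worse in steps, for example 0 to 8 CES-D points, and report the shift at which the conclusion changes. With 25% CMA dropout, a shift of 8 moves the arm difference by 8 × 0.25 = 2 points. Set a corresponding range for PSS in advance.
3. Report post-test completion by arm.

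A common baseline mean is most secure when baseline is measured before allocation. The Overview lists randomisation before the collection of pre-data, while Procedures puts it after the initial assessment, so the two should be reconciled.

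The cost is a few sentences and a little more analysis work, with no added participants or visits. The wording should be settled before results by arm are examined.
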